#### 2.1.8. Statistical power

Sample sizes (n=24 in each group, plus an estimated 12 lost to follow-up) were calculated (G\*POWER) to achieve 95% power at p=.05, 2-sided (t-test), based on a conservative estimate of an effect size (d=1.06) lower than that reported in a previous neurofeedback study of MDD.

Linden et al. (2012) reported a Cohen's d=1.5, with the neurofeedback group displaying a significant decrease (4.13  $\pm$  2.75 from a mean of 14.38 to 10.25 on the Hamilton-17 Depression Rating Scale).

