## 2.1.3. Participants

60 MDD patients (n=24 in each group, plus an estimated 12 lost to follow-up) with insufficient remission of symptoms, patients continue to experience significant symptoms which have not responded to adequate treatment or patients who have not been amenable to adequate treatment. Antidepressant medication is no exclusion criterion, but patients need to be on a stable dose for at least 6 weeks without improvement which they are able to remain on for the duration of the study.

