## 2.1.7. Outcome measures

Primary outcome measure:

 Reduction of depressive symptoms between Visit 1 and 5 as assessed by the Beck Depressive Inventory (BDI-II). (Reduction of depressive symptoms between Visit 1 and the last treatment session as assessed by the Beck Depressive Inventory (BDI-II) for those who do not complete the study.)

Secondary outcome measures:

- 2) Reduction of depressive symptoms between Visit 1 and 5 as assessed by the Montgomery–Asberg Depression Rating Scale (MADRS) by a rater who is blinded to the treatment arm.
- 3) Reduction of self-rated depressive symptoms between Visit 1 and 5 as assessed by the Quick Inventory of Depressive Symptomatology (QIDS-SR 16).
- 4) Clinical Global Impression scale change between Visit 1 and 5 by a rater who is blinded to the treatment arm.
- 5) Withdrawal rates and adverse events after first treatment session.
- 6) Decrease in post vs. pre-training right ATL-SSCR correlation on fMRI (in neurofeedback arm).
- 7) Reductions in implicit self-blaming bias (self-contempt bias BIAT) between Visit 1 and 5.
- 8) Increase in Rosenberg Self Esteem Scale score between Visit 1 and Visit 5.

- 9) Positive Affect score increase and Negative Affect score decrease (PANAS scale) between Visit 1 and Visit 5.
- 10) Profile of Mood States (POMS) depression score change between Visit 1 and 5.
- 11) Self-blame ratings obtained prior to the first and after the last treatment session.
- 12) Reductions in agency-incongruent self-blame on short version of the value-related moral sentiment task between Visit 1 and 5.
- 13) Dysfunctional Attitudes Scale (prior & post mood induction if time permits) between Visit 1 and 5.
- 14) Self- & observer rated clinical global impression on Visit 5 for change since Visit 1.

We may have to drop some of the secondary outcome measures, depending on time constraints.

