#### 2.1.9. Strategy for addressing biases

The trial is fully randomised. Blinding will only be partly possible, but researchers assessing observer-rated outcomes will be blinded to group allocation. Reporting bias will be avoided by a priori definition of design and analyses in a public trial register. We will analyse all collected data of patients lost to follow-up to estimate attrition bias. Partial outcome data for patients lost to follow up will be included in analyses.

#### 2.2. Study 2

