## 4. Diagnostic, Behavioural & Neuropsychological measures

From the following study measures we will select tests and measures which can be feasibly run within the stated time limits. We will therefore test the feasibility in a small group of patients to get a realistic time estimate and insure that patients and healthy controls are not overloaded with testing. All groups will have a baseline assessment of depressive symptoms (BDI-II, MADRS and QID-SR16) and experimental cognitive and emotional tests initially and as part of the post-trial assessment at Visit 5 (see outcome measures). Self-report scales (BDI-II and PANAS) will be carried out after each treatment session.

Clinical evaluation:

- Phone screening for exclusion and inclusion criteria of 15 to 20 minutes, major medical illnesses, substance abuse, axis-I disorders, pregnancy and MRI exclusion criteria, history of psychiatric and neurological treatments
- Non-structured clinical interview (all except healthy volunteers)
- Medical history including GP records if necessary (all)
- Day of menstrual cycle in women to use this as a covariate in the imaging analysis (in the high estrogen phase of the cycle brain activity is largely enhanced which adds variability to the data if not controlled for)
- Age at onset, episode duration, total illness duration
- MDD course: number of episodes, chronic, phasic, medication
- Beck Depression Inventory II (BDI-II; Beck & Brown, 1996)
- Montgomery-Asberg Depression Rating Scale (MADRS; Montgomery & Asberg, 1979)
- Global Social Functioning (GAF) Score (First et al., 2002)

- Psychiatric Family History Screen (Andreasen et al., 1977)
- AMDP Psychopathology Interview questions of depression items (translated from German; Faehndrich & Stieglitz, 1997; 2007)
- Mini International Neuropsychiatric Interview (MINI) suicidality Screen (Sheehan et al., 1998)
- Structured Clinical Diagnostic Interview (SCID)-I. Research Edition (First et al., 2002)
- Life Events Questionnaire (32 items). The scale aims to look at negative and positive life events, those occurring in the past and whether the respondent thinks they have a continuing influence and indicate whether the event was considered 'good', 'neutral' or 'bad'. Adapted from the List of Life Threatening Experiences (LTE; Brugha et al, 1985)
- Clinical Global Impression Scale (Busner & Targum, 2007)
- [LIFE] Longitudinal Interval Follow-up Interview (Keller et al., 1987)

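### The primary outcome is BDI-II change and the only test named is a t-test; adjusting for the Visit 1 BDI-II would make the comparison more precise at almost no cost.

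*Protocol*

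**What the plan says.** Section 2.1.7 of the protocol, like the Study 1 synopsis, gives the primary outcome as "Reduction of depressive symptoms between Visit 1 and 5 as assessed by the Beck Depressive Inventory (BDI-II"), which is a change score. Section 2.1.2 describes the two arms as compared on change between the same two visits.

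Section 2.1.8 holds the only mention of a test. The sample size was calculated "to achieve 95% power at p=.05, 2-sided (t-test"), "based on a conservative estimate of an effect size (d=1.06"), giving "n=24 in each group, plus an estimated 12 lost to follow-up". Section 2.1.3 states the total: "60 MDD patients (n=24 in each group, plus an estimated 12 lost to follow-up").

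The baseline value is available for everyone. Section 4 says: "All groups will have a baseline assessment of depressive symptoms (BDI-II, MADRS and QID-SR16"). That section also mentions the protocol's only covariate, day of menstrual cycle, and it is meant for the imaging analysis.

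Section 2.1.9 places the definition of the analyses elsewhere: "Reporting bias will be avoided by a priori definition of design and analyses in a public trial register".

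**The concern.** Followed as written, sections 2.1.7 and 2.1.8 lead to an unadjusted comparison of mean BDI-II change between arms. That subtracts the Visit 1 score with a coefficient of exactly 1. If the true slope of Visit 5 on Visit 1 is below 1, as it is whenever r is below 1 and the SDs are equal, subtraction over-corrects and leaves avoidable noise in the estimate.

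It also makes the estimate depend on chance baseline imbalance. The arm that happens to start higher will on average show the larger fall. Section 5.1 sets no BDI-II limit for entry, no stratification on severity is described, and with 24 per arm some imbalance is to be expected.

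At stake is the width of the interval in a small pilot trial. There is also a risk of choosing between adjusted and unadjusted results after the data are seen, if the choice is fixed nowhere in advance.

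**Working it through.** **Inputs from the protocol.** 24 evaluable per arm, 12 lost to follow-up, 60 in total, d = 1.06, two-sided alpha 0.05, power 95% (section 2.1.8; total in section 2.1.3).

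**Assumptions, not in the protocol.** The correlation r between Visit 1 and Visit 5 BDI-II is varied from 0.3 to 0.9. The SD s is the same at both visits. The stated d is in units of the SD of change.

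**1. The plan's own figure.** For a two-sample t-test at 24 per arm:
- noncentrality = 1.06 × √(24/2) = 3.67 on 46 df, giving an exact two-sided power of 94.9% (95.7% at 25 per arm);
- the normal approximation gives 24 per arm, with power 95.7%;
- 48/(1 − 0.20) = 60.

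The stated size reproduces. A one-sided test would need only 20 per arm, so the figure matches a two-sided, two-sample t-test.

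**2. Variances.** Per patient:
- change score: Var = 2(1 − r)s²;
- adjusted for baseline: Var = (1 − r²)s²;
- ratio, adjusted to change: (1 − r²)/[2(1 − r)] = (1 + r)/2.

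**3. Price of adjusting.** Estimating the slope takes one degree of freedom (45 instead of 46) and multiplies the variance by about 1 + 1/(2n − 4) = 1 + 1/44 = 1.023 at n = 24 per arm.

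**4. Interval width.** The unadjusted half-width is t(0.975; 46) × √(2/24) = 0.581 SD of change. The relative width after adjustment is √[1.023 × (1 + r)/2] × t(0.975; 45)/t(0.975; 46). At r = 0.5 this is √(1.023 × 0.75) = 0.876, and the change in the t quantile is negligible.

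**5. Power.** The noncentral t is used with d replaced by 1.06/√[1.023 × (1 + r)/2] on 45 df.

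| Assumed r | (1 + r)/2 | Relative CI width | CI narrower by | Power at d = 1.06 (unadjusted 94.9%) |
|---|---|---|---|---|
| 0.3 | 0.65 | 0.816 | 18% | 99.3% |
| 0.5 | 0.75 | 0.876 | 12% | 98.4% |
| 0.7 | 0.85 | 0.933 | 7% | 97.1% |
| 0.8 | 0.90 | 0.960 | 4% | 96.3% |
| 0.9 | 0.95 | 0.986 | 1% | 95.4% |

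At r = 0.95 the width ratio is 0.999, so nothing is gained. In the limit r = 1 the adjusted interval would be 1.2% wider.

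**6. Chance imbalance.** The standard error of a baseline difference between arms is √(2/24) = 0.29 s. Given a baseline difference D, the expected difference in reduction is the true effect plus (1 − r)D. With D = 0.29 s and r = 0.5 the shift is 0.5 × 0.29 s = 0.14 s. At r = 0.5 the SD of change is √[2(1 − 0.5)] s = s, so this is 0.14 SD of change, beside a planned effect of 1.06.

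**The case against.** The strongest objection is that the protocol does not actually name a t-test on BDI-II change as its primary analysis. The t-test appears only as the basis of the sample size, in a sentence that names no outcome. Section 2.1.9 refers the analyses to a public register, and a statistical analysis plan may exist. A reader might infer that the protocol commits itself to an unadjusted analysis. The document does not support that, since nothing in it rules out a covariate. This stands. What remains is that the outcome is fixed as change, that the only test mentioned is unadjusted, and that no clinical covariate appears anywhere.

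Two other readings are tempting and also fail. One is that the Visit 1 score is thrown away. It is not: subtraction uses it with a fixed weight, and only a comparison of Visit 5 scores alone would discard it. The other is that the change-score comparison is biased. Under randomisation it is unbiased and keeps its type I error; the shift in step 6 is conditional on an imbalance that has occurred.

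The size of the gain is also open to challenge. It rests wholly on an assumed r and nearly vanishes at about 0.9. Widely spread baseline scores do not by themselves strengthen the case: for a given within-patient variation, more spread between patients raises r and shrinks the gain. Power at d = 1.06 is already close to 95%, so little power can be added there. All of this stands and limits the point to one of precision.

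**Conclusion.** The point holds as a recommendation on efficiency. At 24 per arm, with equal SDs, adjusting for Visit 1 BDI-II narrows the 95% interval by about 18% at r = 0.3, 12% at r = 0.5 and 4% at r = 0.8, with about 1% left at r = 0.9. It also removes the dependence of the estimate on chance baseline imbalance, as far as the relation is linear.

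A reader might infer that the sample size is wrong. It is not: it reproduces, and sizing on an unadjusted t-test is compatible with an adjusted analysis and normally conservative.

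The figures take 24 per arm as analysed. Section 2.1.7 gives non-completers an outcome at their last treatment session, and section 2.1.9 includes partial data, so the analysed number may exceed 48, up to 60. The relative gain depends mainly on r and changes little with that number.

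**What to change.** Add one sentence to the protocol, the register entry or the analysis plan. It should say that the primary comparison is Visit 5 BDI-II (or the change from Visit 1) adjusted for Visit 1 BDI-II by ANCOVA, or by the same baseline term in a repeated-measures model, and reported as an adjusted mean difference with its 95% confidence interval. With baseline as covariate, ANCOVA of the Visit 5 score and of the change gives the same treatment effect, so the outcome can still be described as a reduction.

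Use the same form for continuous secondary outcomes that have a Visit 1 value in both arms, such as MADRS, QIDS-SR 16, Rosenberg, PANAS and POMS. It does not apply to item 6, which is measured in the neurofeedback arm only, or to item 14, which rates change directly and has no Visit 1 value.

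The cost is one degree of freedom and a slope-estimation penalty of about 1% of the interval width, already counted above. No new data are needed, and the sample size stays as it is.

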#### 2.1.9. Strategy for addressing biases

The trial is fully randomised. Blinding will only be partly possible, but researchers assessing observer-rated outcomes will be blinded to group allocation. Reporting bias will be avoided by a priori definition of design and analyses in a public trial register. We will analyse all collected data of patients lost to follow-up to estimate attrition bias. Partial outcome data for patients lost to follow up will be included in analyses.

#### 2.2. Study 2

#### 2.2.1. Specific aim and hypothesis

Case-control study to investigate neurocognitive mechanisms underpinning self-blame bias in major depressive disorder compared with panic disorder and healthy control participants. This study will gather the first evidence how specific self-blaming biases previously demonstrated in MDD (Green et al., 2013) are when compared with another mental health disorder. Further, a novel experimental task will be applied investigating whether changes in social agency inferences underpin self-blaming biases in MDD. We hypothesise that patients with MDD show self-blaming emotional biases and overgeneralisation of self-agency for failure when compared with panic disorder and healthy control participants. In case participants perceive the implied neurocognitive testing as emotionally distressing, they are offered consultation by a psychiatrist.

#### 2.2.2. Participants

Two control groups: Panic disorder patients (n=30, including 5 dropouts) with insufficient remission, with no history of MDD. Antidepressant medication will be allowed to be comparable with the MDD group. Healthy control participants with no personal or family history of mood, anxiety disorders or schizophrenia: (n=30, including 5 dropouts), melancholic MDD (n=30, including 5 dropouts), MDD with no specifiers (n=30, including 5 dropouts). MDD participants will be either specifically recruited for this study or their data will derive from participation in study 1.

## **3.** General Experimental Procedures

Patients insufficiently remitted from MDD for at least six weeks, healthy volunteers and subjects with insufficient remission of panic disorder will be recruited through radio and newspaper adverts, internet adverts, flyers posted to university bulletin boards and e-mail advertisements as well as sent to self-help groups. We will also send out flyers to general practitioners and specialists and recruit through GP practices after obtaining primary care R&D approval.

- Patients referred from doctors will be evaluated clinically or by phone to screen for inclusion and exclusion criteria. Participants responding to adverts will be prescreened for inclusion and exclusion criteria by a phone interview, they will be asked for permission for conducting the phone interview at the beginning of the conversation by reading the following statement to them: 'I would like to do a short phone interview with you, which will take around 15 minutes. This is necessary to see whether some conditions rule out that we can include you into the study. You will be asked questions about psychiatric, neurological and medical symptoms, treatments, learning problems and whether such symptoms occurred in your family. I will also ask about substance or alcohol abuse. Things which are an obstacle to participate in MRI studies such as possible pregnancy or metallic objects will also be asked. Results of these questions will not be stored, but we ask your permission to store your contact information and whether you passed the screening for the study group in an electronic database which is protected by a password and can only be accessed by the investigators.'
- For the case-control study (study 2) we may offer participants to complete electronic questionnaires by e-mail. Consent forms will be sent to them for printing out and participants are asked to sign them and send a scanned copy back to us as an e-mail attachment, a fax or by regular mail. They will send completed electronic questionnaires by e-mail. Those questionnaires will contain no personally identifiable information.
- During the first session scheduled after screening for inclusion and exclusion criteria, standardised psychiatric assessments as well as self- and observer-report scales will be used to assess neuropsychiatric symptoms and to verify the clinical diagnosis. Clinical evaluation may take up to 2 hours and follows standard practice. Diagnostic interviews and scales will be limited to a maximum of 3 hours.
- In the fMRI neurofeedback condition, a separate session in a mock scanner may be arranged for people with no experience in MRI scanning to get familiar with the environment.
- At each visit, before and after the treatment session, patients will receive standardised scales to assess measures of individual differences on mood, cognition and personality. The researcher will alert the psychiatrist if the BDI-II suicidality item is rated above 0 and the subsequent Mini International Psychiatric Interview suicidality module results in a score indicating more than a low risk. The psychiatrist will then offer a consultation and decide with the patient whether to continue with the study.
- Participants will perform practice tasks prior to the MRI. This preparation may take up to 45 minutes. Scanning, including clinical, structural and functional scans will take 1 hour but may exceed that time in case of technical difficulties and if the patient/subject is willing to continue for up to 90 minutes, in very rare occasions 120 minutes. After the scanning participants perform computerised tests to correlate performance during the MRI scanning with performance outside of the scanner. This testing may take up to 1 hour.
- On two separately scheduled testing days (pre- and post-trial assessment, Visits 1 & 5), patients will perform neuropsychological tasks or give computerised self-report

ratings on mood, cognition and personality as well as on the stimuli delivered during MRI. These ratings may also be sent out as files to be completed by e-mail and returned by e-mail. Personally identifiable information will not be contained in the files exchanged by e-mail. Testing will be limited to 3 hours per day for patients and up to 4 hours per day for normal subjects, breaks will be planned depending on the needs of the participant.

- Following the post-trial assessment at Visit 5, the participant's GP will be notified about the results of relevant clinical measures.
- All patients and healthy subjects will be asked to give consent for being recontacted by mail, e-mail or phone to take part in additional longitudinal follow-up evaluations including further imaging and/or neuropsychological evaluation. Longitudinal followup studies allow us to study the predictive value of our neuropsychological and imaging measures to predict later clinical outcome and to test the re-test reliability of the employed measures. The realisation of longitudinal follow-up studies will depend on the success of further grant applications.
- Participants will receive reimbursement for time and travel expenses after their final participation day in the study. Participants are compensated in form of High Street gift vouchers or Shopping vouchers: £10 for pre-trial assessment session (Visit 1), £20 per treatment session (3x£20 = £60 for Visit 2, Visit 3, Visit 4), £30 for final follow-up session (Visit 5).
- If requested, participants will be informed of the final results after completion of the study.

These methodological details apply to all of the experiments proposed below, except where otherwise stated.

## 4. Diagnostic, Behavioural & Neuropsychological measures

From the following study measures we will select tests and measures which can be feasibly run within the stated time limits. We will therefore test the feasibility in a small group of patients to get a realistic time estimate and insure that patients and healthy controls are not overloaded with testing. All groups will have a baseline assessment of depressive symptoms (BDI-II, MADRS and QID-SR16) and experimental cognitive and emotional tests initially and as part of the post-trial assessment at Visit 5 (see outcome measures). Self-report scales (BDI-II and PANAS) will be carried out after each treatment session.

Clinical evaluation:

- Phone screening for exclusion and inclusion criteria of 15 to 20 minutes, major medical illnesses, substance abuse, axis-I disorders, pregnancy and MRI exclusion criteria, history of psychiatric and neurological treatments
- Non-structured clinical interview (all except healthy volunteers)
- Medical history including GP records if necessary (all)
- Day of menstrual cycle in women to use this as a covariate in the imaging analysis (in the high estrogen phase of the cycle brain activity is largely enhanced which adds variability to the data if not controlled for)
- Age at onset, episode duration, total illness duration
- MDD course: number of episodes, chronic, phasic, medication
- Beck Depression Inventory II (BDI-II; Beck & Brown, 1996)
- Montgomery-Asberg Depression Rating Scale (MADRS; Montgomery & Asberg, 1979)
- Global Social Functioning (GAF) Score (First et al., 2002)

- Psychiatric Family History Screen (Andreasen et al., 1977)
- AMDP Psychopathology Interview questions of depression items (translated from German; Faehndrich & Stieglitz, 1997; 2007)
- Mini International Neuropsychiatric Interview (MINI) suicidality Screen (Sheehan et al., 1998)
- Structured Clinical Diagnostic Interview (SCID)-I. Research Edition (First et al., 2002)
- Life Events Questionnaire (32 items). The scale aims to look at negative and positive life events, those occurring in the past and whether the respondent thinks they have a continuing influence and indicate whether the event was considered 'good', 'neutral' or 'bad'. Adapted from the List of Life Threatening Experiences (LTE; Brugha et al, 1985)
- Clinical Global Impression Scale (Busner & Targum, 2007)
- [LIFE] Longitudinal Interval Follow-up Interview (Keller et al., 1987)
- Maudsley modified PHQ-9 (for validation, based on modification of the standard PHQ-9 as used in primary care).

